6.1.2.6.1 Initial Tumor Imaging

Initial tumor imaging at Screening must be performed within 21 days prior to the date of allocation. The site study team must review screening images to confirm the participant has measurable disease per RECIST 1.1.

The screening images must be submitted to the central imaging vendor for confirmation of measurable disease per RECIST 1.1 for eligibility prior to allocation.

Brain imaging, if performed to document the stability of existing metastases, should be by MRI if possible. If MRI is medically contraindicated, CT with contrast is an acceptable alternative.

6.1.2.6.2 Tumor Imaging During the Study

The first on-study imaging assessment should be performed at 9 weeks (± 7 days) from the date of first dose. Subsequent tumor imaging should be performed every 9 weeks (± 7 days) or more frequently if clinically indicated. After 52 weeks (± 7 days), participants who remain on treatment will have imaging performed every 12 weeks (± 7 days). Imaging timing should follow calendar days and should not be

adjusted for delays in cycle starts. Imaging should continue to be performed until disease progression is identified by the Investigator.

Objective response should be confirmed by a repeat imaging assessment. Tumor imaging to confirm PR or CR should be performed at least 4 weeks after the first indication of a response is observed. Participants will then return to regular scheduled imaging every 9 weeks, starting with the next scheduled imaging time point. Participants who receive additional imaging for confirmation do not need to undergo the next scheduled tumor imaging if it is less than 4 weeks later; tumor imaging may resume at the subsequent scheduled imaging time point.

Per iRECIST (Section 7.1.2.6.6), disease progression should be confirmed by the site 4 to 8 weeks after first radiologic evidence of PD in clinically stable participants. Participants who have unconfirmed disease progression may continue on treatment at the discretion of the investigator until progression is confirmed by the site provided they have met the conditions detailed in Section 7.1.2.6.6. Participants who receive confirmatory imaging do not need to undergo the next scheduled tumor imaging if it is less than 4 weeks later; tumor imaging may resume at the 1.2.6.6.subsequent scheduled imaging time point, if clinically stable. Participants who have confirmed disease progression by iRECIST, as assessed by the site, will discontinue study treatment. Exceptions are detailed in Section 7.

6.1.2.6.3 End of Treatment and Follow-up Tumor Imaging

In participants who discontinue study treatment, tumor imaging should be performed at the time of treatment discontinuation (± 4 week window). If previous imaging was obtained within 4 weeks prior to the date of discontinuation, then imaging at treatment discontinuation is not mandatory. In participants who discontinue study treatment due to documented disease progression and the investigator elects not to implement iRECIST, this is the final required tumor imaging.

For participants who discontinue study treatment without documented disease progression, every effort should be made to continue monitoring their disease status by tumor imaging using the same imaging schedule used while on treatment (every 9 weeks in Year 1 or every 12 weeks after Year 1) to monitor disease status until the start of a new anticancer treatment, disease progression, pregnancy, death, withdrawal of consent, or the end of the study, whichever occurs first.

6.1.2.6.4 Second Course (Retreatment) Tumor Imaging

Tumor imaging must be performed within 21 days prior to restarting treatment with pembrolizumab. Local reading (Investigator assessment with site radiology reading) will be used to determine eligibility.

The first on-study imaging assessment should be performed at 9 weeks (± 7 days) after the restart of treatment. Subsequent tumor imaging should be performed every 9 weeks (± 7 days) or more frequently, if clinically indicated.

Per RECIST 1.1 (Section 7.1.2.6.5), if tumor imaging shows initial PD, tumor assessment should be repeated 4 to 8 weeks later in order to confirm PD with the option of continuing treatment while awaiting radiologic confirmation of progression with the option of continuing treatment while awaiting radiological confirmation of progression in clinically stable patients. Participants who obtain confirmatory imaging do not need to undergo scheduled tumor imaging if it is less than 4 weeks later and may wait until the next scheduled imaging time point, if clinically stable.

Imaging should continue to be performed until disease progression, the start of a new anticancer treatment, withdrawal of consent, death, or notification by the Sponsor, whichever occurs first. Disease progression may be confirmed 4 to 8 weeks after the first tumor imaging indicating PD, by the investigator using iRECIST, in clinically stable participants.

In participants who discontinue study treatment, tumor imaging should be performed at the time of treatment discontinuation (± 4 week window). If previous imaging was obtained within 4 weeks prior to the date of discontinuation, then imaging at treatment discontinuation is not mandatory. For participants who discontinue study treatment due to documented disease progression, this is the final required tumor imaging.

For participants who discontinue study treatment without documented disease progression, every effort should be made to continue monitoring their disease status by radiologic imaging every 12 weeks (± 7 days) until either the start of a new anticancer treatment, disease progression, pregnancy, death, or the end of the study, whichever occurs first.

6.1.2.6.5 RECIST 1.1 Assessment of Disease

RECIST 1.1 will be used as the primary measure for assessment of tumor response, date of disease progression, and as a basis for all protocol guidelines related to disease status (eg, discontinuation of study treatment). Although RECIST 1.1 references a maximum of 5 target lesions in total and 2 per organ, the Sponsor allows a maximum of 10 target lesions in total and 5 per organ, if clinically relevant to enable a broader sampling of tumor burden.

6.1.2.6.6 iRECIST Assessment of Disease

iRECIST is based on RECIST 1.1 but adapted to account for the unique tumor response seen with immunotherapeutic drugs. When clinically stable, participants should not be discontinued until progression is confirmed by the Investigator, working with local radiology, according to the rules below. This allowance to continue treatment despite initial radiologic PD takes into account the observation that some participants can have a transient tumor flare in the first few months after the start of immunotherapy, and then experience subsequent disease response.

[figure not shown]
A description of the adaptations and iRECIST process is provided in Appendix 4, with additional detail in the iRECIST publication [Seymour et al., 2017]. iRECIST will be used by the Investigator to assess tumor response and progression, and make treatment decisions.

Table 8 Imaging and Treatment after First Radiologic Evidence of Progressive Disease

	Clinically Stable		Clinically Unstable	
	Imaging	Treatment	Imaging	Treatment
First radiologic evidence of PD by RECIST 1.1	Repeat imaging at 4 to 8 weeks to confirm PD	May continue study treatment at the Investigator's discretion while awaiting confirmatory tumor imaging by site by iRECIST	Repeat imaging at 4 to 8 weeks to confirm PD per Investigator's discretion only	Discontinue treatment
Repeat tumor imaging confirms PD (iCPD) by iRECIST per Investigator assessment	No additional imaging required	Discontinue treatment (exception is possible upon consultation with Sponsor)	No additional imaging required.	Not applicable
Repeat tumor imaging shows iUPD by iRECIST per Investigator assessment	Repeat imaging at 4 to 8 weeks to confirm PD. May occur at next regularly scheduled imaging visit	Continue study treatment at the Investigator's discretion	Repeat imaging at 4 to 8 weeks to confirm PD per Investigator's discretion only	Discontinue treatment
Repeat tumor imaging shows iSD, iPR, or iCR by iRECIST per Investigator assessment.	Continue regularly scheduled imaging assessments	Continue study treatment at the Investigator's discretion	Continue regularly scheduled imaging assessments.	May restart study treatment if condition has improved and/or clinically stable per Investigator's discretion. Next tumor imaging should occur according to the regular imaging schedule.

iCPD = iRECIST confirmed progressive disease; iCR = iRECIST complete response; iRECIST = modified Response Evaluation Criteria in Solid Tumors 1.1 for immune-based therapeutics; iSD = iRECIST stable disease; iUPD = iRECIST unconfirmed progressive disease; PD = progressive disease; RECIST 1.1 = Response Evaluation Criteria in Solid Tumors 1.1..

Figure 1: Imaging and Treatment for Clinically Stable Participants after First Radiologic Evidence of PD Assessed by the Investigator

6.1.2.7 Tumor Tissue Collection and Correlative Studies Blood Sampling

Formalin fixed paraffin embedded (FFPE) tissue will be obtained from patients participating in the trial. The presence of archival tumor material is part of the criteria for eligibility for this trial.

Stools will be collected prior to the beginning of treatment (within 7 days), after two treatment cycles (prior to the third dose of pembrolizumab) and at the end of treatment.

6.1.3 Laboratory Procedures/Assessments

Details regarding specific laboratory procedures/assessments to be performed in this trial are provided below.

Laboratory tests for hematology, chemistry, urinalysis, and others are specified in Table 9.

Table 9 Laboratory Tests

Hematology	Chemistry	Urinalysis	Other
Hematocrit	Albumin	Blood	Serum β -human chorionic gonadotropin†
Hemoglobin	Alkaline phosphatase	Glucose	(β -hCG)†
Platelet count	Alanine aminotransferase (ALT)	Protein	PT (INR)
WBC (total and differential)	Aspartate aminotransferase (AST)	Specific gravity	aPTT
Red Blood Cell Count	Lactate dehydrogenase (LDH)	Microscopic exam (If abnormal)	Total triiodothyronine (T3)
Absolute Neutrophil Count	Carbon Dioxide ‡	results are noted	Free tyroxine (T4)
Absolute Lymphocyte Count	(CO_2 or bicarbonate)	Urine pregnancy test †	Thyroid stimulating hormone (TSH)
	Uric Acid		PK
	Calcium		
	Chloride		Stools for correlative studies
	Glucose		
	Phosphorus		
	Potassium		
	Sodium		
	Magnesium		
	Total Bilirubin		
	Direct Bilirubin (If total bilirubin is elevated above the upper limit of normal)		
	Total protein		
	Blood Urea Nitrogen		

† Perform on women of childbearing potential only. If urine pregnancy results cannot be confirmed as negative, a serum pregnancy test will be required.

‡ If considered standard of care in your region.

Table 10 Laboratory safety variables

Haematology/Haemostasis (whole blood)	Clinical Chemistry (serum or plasma)
B-Hemoglobin (Hb)	S/P-Creatinine
B-Leukocyte count	S/P-Bilirubin, total
B-Absolute neutrophil count	S/P-Alkaline phosphatase (ALP)
B-Absolute lymphocyte count	S/P-Aspartate transaminase (AST)
B-Platelet count	S/P-Alanine transaminase (ALT)
B-Mean cell volume (MCV)	S/P-Albumin
	S/P-Potassium
	S/P-Calcium, total
	S/P-Sodium
Urinalysis (dipstick)	S/P-Urea or Blood Urea Nitrogen (BUN)
U-Hb/Erythrocytes/Blood	S/P-Total Protein
U-Protein/Albumin	
U-Glucose	

NB. In case a patient shows an AST **or** ALT $\geq 3 \times \text{ULN}$ together with total bilirubin $\geq 2 \times \text{ULN}$ please refer to Appendix E ‘Actions required in cases of increases in liver biochemistry and evaluation of Hy’s Law’, for further instructions.

6.1.3.1 Coagulation

- activated partial thromboplastin time {APTT} will be performed at screening and if clinically indicated
- international normalised ratio {INR} will be performed at screening and if clinically indicated. Patients taking warfarin may participate in this study; however, it is recommended that INR be monitored carefully at least once per week for the first month, then monthly if the INR is stable.

Each coagulation test result will be recorded in CRF.

6.1.3.2 Bone marrow or blood cytogenetic samples

Bone marrow or blood cytogenetic samples may be collected for patients with prolonged hematological toxicities as defined in Section 8.4.7 per routine medical oncology at Miami Cancer Institute.

Bone marrow analysis should include an aspirate for cellular morphology, cytogenetic analysis and flow cytometry, and a core biopsy for bone marrow cellularity. If it is not possible to conduct cytogenetic analysis or flow cytometry on the bone marrow aspirate, then attempts should be made to carry out the tests on a blood sample. Full reports must be provided by the investigator for documentation on the Patient Safety database. These data are not required to be entered into CRF.

Laboratory tests for screening or entry into the Second Course Phase should be performed within 10 days prior to the first dose of treatment. After Cycle 1, pre-dose laboratory procedures can be conducted up to 72 hours prior to dosing. Results must be reviewed by the investigator or qualified designee and found to be acceptable prior to each dose of trial treatment.

6.1.4 Other Procedures

6.1.4.1 Discontinuation and withdrawal

When a participant discontinues prior to trial completion, all applicable activities scheduled for the final trial visit should be performed at the time of discontinuation. Any adverse events which are present at the time of discontinuation should be followed in accordance with the safety requirements outlined in Section 7.2. - Assessing and Recording Adverse Events. Participants who a) attain a CR or b) complete 24 months of treatment with pembrolizumab may discontinue treatment with the option of restarting treatment if they meet the criteria specified in Section 5.2.3. After discontinuing treatment following assessment of CR, these participants should return to the site for a Safety Follow-up Visit (described in Section 7.1.5.3.1) and then proceed to the Follow-Up Period of the study (described in Section 7.1.5.3.2).

Participants who withdraw prior to completion of the trial should be encouraged to complete all applicable activities scheduled for the final study visit at the time of withdrawal. Any AEs that are present at the time of withdrawal should be followed in accordance with the safety requirements outlined in Section 7.2.

6.1.4.2 Withdrawal from Future Biomedical Research

Participants may withdraw their consent for future biomedical research. Participants may withdraw consent at any time by contacting the investigator. The investigator will inform the Sponsor. It is the responsibility of the investigator to subsequently inform the participant of completion of withdrawal. Any analyses in progress at the time of request for withdrawal or already performed prior to the request for withdrawal being received will continue to be used as part of the overall research study data and results. No new analyses should be generated after the request is received.

In the event that the specimens have been completely anonymized, there will be no link between the participant's personal information and their specimens. In this situation, the request for specimen withdrawal cannot be processed.

6.1.5 Visit Requirements

Visit requirements are outlined in Section 6.0 - Trial Flow Chart. Specific procedure-related details are provided above in Section 7.1 - Trial Procedures.

6.1.5.1 Screening

6.1.5.1.1 Screening Period

6.1.5.2 Treatment Period

6.1.5.3 Post-Treatment Visits

6.1.5.3.1 Safety Follow-Up Visit

The mandatory Safety Follow-Up Visit should be conducted approximately 30 days after the last dose of study treatment or before the initiation of a new anti-cancer treatment, whichever comes first. All AEs that occur prior to the Safety Follow-Up Visit should be recorded. Participants with an AE of Grade > 1 will be followed until the resolution of the AE to Grade 0-1 or until the beginning of a new anti-cancer therapy, whichever occurs first. SAEs that occur within 90 days of the end of treatment or before initiation of a new anti-cancer treatment should also be followed and recorded. Participants who are eligible for retreatment/crossover with pembrolizumab (as described in Section 5.2.3) may have up to two safety follow-up visits, one after the Initial Treatment Period and one after the Second Course Treatment.

6.1.5.3.2 Follow-up Visits

Participants who discontinue study treatment for a reason other than disease progression will move into the Follow-Up Phase and should be assessed every 6 weeks (42 ± 7 days) by radiologic imaging to monitor disease status. After 1 year, the imaging time point will occur every 9 weeks (± 7 days). Every effort should be made to collect information regarding disease status until the start of new anti-cancer therapy, disease progression, death, end of the study or if the participant begins retreatment with pembrolizumab as detailed in Section 5.2.3. Information regarding post-study anti-cancer treatment will be collected if new treatment is initiated.

Participants who are eligible to receive retreatment with pembrolizumab according to the criteria in Section 5.2.3 will move from the follow-up phase to the Second Course Phase when they experience disease progression.

6.1.5.3.3 Survival Follow-up

Participants who experience confirmed disease progression or start a new anticancer therapy, will move into the Survival Follow-Up Phase and should be contacted by telephone every 12 weeks to assess for survival status until death, withdrawal of consent, or the end of the trial, whichever occurs first.

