1.0 TRIAL SUMMARY

Abbreviated Title	Pembrolizumab and Olaparib in Cervical Cancer Patients
Trial Phase	II
Clinical Indication	Cervical Cancer
Trial Type	Therapeutic
Type of control	None
Route of administration	Intravenous and Oral
Trial Blinding	None
Treatment Groups	One
Number of trial participants	48
Estimated enrollment period	2-3 years
Estimated duration of trial	3-4 years
Duration of Participation	Until lack of clinical benefit is demonstrated.
Estimated average length of treatment per patient	6 months

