six patients. If intolerable toxicities arise after three or more cycles in patients otherwise experiencing clinical benefit, patients will have the option of continue pembrolizumab as monotherapy. Special attention will be placed on persistent grade 3 or higher anemia, as myelodysplastic syndromes have been described in around 1.5% of patients receiving olaparib in previous trials[Pujade-Lauraine et al., 2017; Robson et al., 2017; Ledermann et al., 2012; Moore et al., 2014]. Hematologic consultation (with bone marrow aspiration as needed) will be requested for patients developing persistent anemia.

Patients will be followed for three (3) years or until time of death. ORR, PFS, and OS will be determined. Correlative studies will determine the functional status of the Fanconi Anemia pathway promoting homologous recombination repair as well as the microbiome composition in responsive and non-responsive patients. In addition, tumor mutation burden, MSI, and PD-L1 expression will be correlated with Fanconi Anemia pathway status and response to therapy.

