Note: The number of treatments is calculated starting with the first dose. Participants who stop the combination or pembrolizumab after receiving 35 doses may be eligible for retreatment if they progress after stopping study treatment provided they meet the requirements detailed in Section 5.2.3. Participants may be retreated in the Second Course Phase (Retreatment) for up to an additional 17 cycles (approximately 1 year).

- Administrative reasons
- The End of Treatment and Follow-up visit procedures are listed in Section 8 (Protocol Flow Chart) and Section 10.0.1 (Visit Requirements). After the end of treatment, each subject will be followed for 30 days for adverse event monitoring (serious adverse events will be collected for 90 days after the end of treatment). Subjects who discontinue for reasons other than progressive disease will have post-treatment follow-up for disease status until disease progression, initiating a non-study cancer treatment, withdrawing consent or becoming lost to follow-up. After documented disease progression each subject will be followed by telephone for overall survival until death, withdrawal of consent, or the end of the study, whichever occurs first.

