- All AEs meeting serious criteria, from the time of intervention allocation/randomization through 90 days following cessation of study intervention or 30 days following cessation of study intervention if the participant initiates new anticancer therapy, whichever is earlier, must be reported by the investigator.
- All pregnancies and exposure during breastfeeding, from the time of intervention allocation/randomization through 120 days following cessation of study intervention, or 30 days following cessation of study intervention if the participant initiates new anticancer therapy must be reported by the investigator.
- Additionally, any SAE brought to the attention of an investigator at any time outside of the time period specified above must be reported immediately to Merck if the event is considered drug-related.

Investigators are not obligated to actively seek AEs or SAEs or other reportable safety events in former study participants. However, if the investigator learns of any SAE, including a death, at any time after a participant has been discharged from the study, and he/she considers the event to be reasonably related to the study intervention or study participation, the investigator must promptly notify Merck.

All initial and follow-up AEs, SAEs, and other reportable safety events will be recorded and reported to Merck within the time frames as indicated in Table 11.

Table 11 Reporting Time Periods and Time Frames for Adverse Events and Other Reportable Safety Events

Type of Event	Reporting Time Period: Consent to Randomization/Allocation	Reporting Time Period: Randomization/Allocation through Protocol-specified Follow-up Period	Reporting Time Period: After the Protocol-specified Follow-up Period	Time Frame to Report Event and Follow-up Information to Merck:
Serious Adverse Event (SAE) including Cancer and Overdose	Report if: - due to protocol-specified intervention - causes exclusion - participant is receiving placebo run-in or other run-in treatment	Report all	Report if: - drug/vaccine related. (Follow ongoing to outcome)	Within 2 business days but no longer than 3 calendar days of learning of event
Pregnancy/Lactation Exposure	Report if: - due to intervention - causes exclusion	Report all	Previously reported – Follow to completion/termination; report outcome	Within 2 business days but no longer than 3 calendar days of learning of event

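### After the SAE window closes, no scheduled contact asks about MDS, AML or another new malignancy, so a diagnosed late case may go unrecorded

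*Combined protocol and SAP*

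**What the plan says.** Section 2.0 identifies the harm: "Special attention will be placed on persistent grade 3 or higher anemia, as myelodysplastic syndromes have been described in around 1.5% of patients" given olaparib in earlier trials. Section 4.2.2 repeats this, and 6.2.1.1 makes confirmed MDS reportable as an SAE. The same section 2.0 sets the length of follow-up: "Patients will be followed for three (3) years or until time of death".

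Safety collection ends earlier. Ordinary AEs are reported to 30 days after treatment (6.2.1). Section 5.6 says "serious adverse events will be collected for 90 days after the end of treatment". Section 6.2.1 is more specific and sets SAE reporting "through 90 days following cessation of study intervention or 30 days following cessation of study intervention if the participant initiates new anticancer therapy", whichever comes first. Outside that window, an SAE that comes to the investigator's attention "must be reported immediately to Merck if the event is considered drug-related".

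Two kinds of contact remain after treatment:

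- **Follow-up visits (6.1.5.3.2).** Patients who stopped without progression have imaging for disease status, and any new anticancer treatment is recorded.
- **Survival follow-up (6.1.5.3.3).** Patients with confirmed progression or new therapy "should be contacted by telephone every 12 weeks to assess for survival status". Section 5.6 agrees: "After documented disease progression each subject will be followed by telephone for overall survival until death". Calls stop at death, withdrawal of consent or the end of the trial.

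In the Schedule of Activities (2.3), the later contacts carry post-study therapy status and survival status. AE review appears only under the treatment cycles.

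**The concern.** MDS and AML can be diagnosed after treatment has stopped. The protocol names MDS, gives a rate for it and stays in touch with patients for up to three years, yet none of the later contacts includes a question about it. Once the window closes, a diagnosis has to reach the investigator unprompted and then be judged drug-related. Patients may have had up to two prior chemotherapy regimens (5.1.1) and may receive more later, so attribution of a late MDS could be uncertain and the case could fail that second step.

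What is at stake is how the safety report can be read. If it shows no late cases, a reader cannot tell whether none was diagnosed or nobody asked. This bears on the secondary safety objective (3.2). It does not touch the iORR decision.

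**Working it through.** **Figures in the plan.** The plan gives no sample-size or precision figure for MDS/AML. Its one design calculation is the response rule (48 patients, 10 or more responses, 0.130 against 0.280). Exact binomial error rates are 0.0865 and 0.0995, against the stated 0.087 and 0.099. That rule reproduces and is unaffected by this point.

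**Step 1: is there any solicited route after the window?**

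- 6.1.2.1 says in general terms that AEs are recorded in the follow-up period as well. It ties assessment to the flow chart, which as far as it can be read shows AE review only in the cycles. The explicit limits in 6.2.1 also cut it off.
- 6.2.3 requires active follow-up of events, cancer included, but only once an initial report exists.
- 6.2.1.1 places the MDS reporting rule under a heading about hematological toxicity during treatment.
- Appendix 5 (14.1.3) puts new cancers on the SAE reporting track, but adds no question at any contact.
- 6.1.1.6.3 and 6.1.5.3.2 collect later anticancer therapy. That could reveal treated AML or MDS, but not disease that is untreated or given supportive care only.

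None of these asks for the diagnosis.

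**Step 2: how much follow-up time is affected?** Inputs: three years of follow-up (2.0), assumed to run from treatment start; 6 months as the "Estimated average length of treatment per patient" (1.0); 24 months as the pembrolizumab limit (5.2.1); a window of 3 months, or 1 month with new therapy (6.2.1). The patient is assumed alive and in contact at 36 months.

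Unsolicited months = 36 − (treatment + window).

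| Treatment | 3-month window | 1-month window (new therapy) |
|---|---|---|
| 6 months | 36 − 9 = 27 (75%) | 36 − 7 = 29 (81%) |
| 24 months | 36 − 27 = 9 (25%) | 36 − 25 = 11 (31%) |

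Three things shorten these times. Early death ends exposure. A second course (5.2.3) extends treatment. Calls also stop at trial end: with 2–3 years of enrollment and 3–4 years in total (1.0), a patient who starts at the end of year 3 of a four-year trial has 12 months in all. At 6 months of treatment that leaves 12 − 9 = 3 months, or 12 − 7 = 5 with new therapy.

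**Step 3: how many cases?** At the cited 1.5%, the expected total is 48 × 0.015 = 0.72, and the chance of at least one is 1 − (1 − 0.015)^48 = 51.6%. These figures include cases arising on treatment, which existing rules already capture, and make no allowance for competing death. At that rate they are ceilings for late cases. With an assumed rate of 0.5%, the expected total is 48 × 0.005 = 0.24. The documents give no distribution of onset times, so the late share, and hence the number missed, cannot be derived.

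**Step 4: what would one missed case change?** One case is 1/48 = 2.1% (exact 95% CI 0.05% to 11.1%). None is 0/48, with upper limit 1 − 0.025^(1/48) = 7.4%. Both intervals contain 1.5%.

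**The case against.** The case for leaving the plan alone has real content.

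- **Some patients are already watched.** An AE above Grade 1 is followed until it resolves or new therapy starts (6.1.5.3.1), and persistent anemia or prolonged cytopenia leads to hematology referral (2.0, 6.2.1.1). A patient who leaves treatment with an unresolved cytopenia is therefore under active follow-up. This stands and narrows the gap, though new therapy ends the 6.1.5.3.1 follow-up.
- **Section 7.2 is not limited to TEAEs.** It also plans separate summaries of serious and drug-related AEs, and a late case reported passively could appear there. This stands, but a summary can show only what was collected.
- **Table 11 asks for all SAEs, cancer included, through the protocol's follow-up period.** The text just above the table gives the 90/30-day windows, which supply a workable meaning. I do not raise it as a separate point.
- **Limiting solicited collection is a stated choice** in a 48-patient, single-arm phase II trial with response as the endpoint, and a long-term MDS/AML count is not an objective. This also stands: the plan is not in error.

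A reader might infer that 6.2.1 tells sites not to ask patients on survival calls, because it says investigators need not seek out events. That sentence concerns former participants, and 5.6 says that stopping treatment is not withdrawal from the study. The point rests instead on the collection windows and on what the contacts contain.

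**Conclusion.** The point holds as an optional improvement to safety ascertainment. After 90 days (30 with new therapy), a late MDS/AML diagnosis depends on passive reporting filtered by attribution, although contact with the patient continues. Unsolicited time is 9 to 29 of 36 months for a patient alive and in contact at three years, depending on treatment length and later therapy, and less for early deaths and late enrollees. Fewer than one case is expected in total at the cited rate.

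Three stronger readings are not supported:

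- That most follow-up is uncovered for patients generally. The 75% to 81% figures pair average treatment length with three-year survival, and long survivors may well be treated for longer.
- That the trial will miss cases, or some stated number of them. No onset data are given, and a late case that reaches the investigator and is judged drug-related must be reported at any time.
- That a trial conclusion is at risk. The iORR decision and the TEAE tables do not change, and one case more or less leaves the interval compatible with 1.5%.

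The time calculation assumes that the three years run from treatment start. The case count assumes that the cited olaparib rate applies to this population.

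**What to change.** In 6.1.5.3.2 and 6.1.5.3.3, ask at each existing follow-up visit and each 12-weekly call whether MDS, AML or another new malignancy has been diagnosed. Record any case in the CRF regardless of attribution or new therapy, with the diagnosis date and the anticancer therapies given in between. In 7.2, add a listing (n/N) of diagnosed cases over all follow-up, kept apart from the TEAE tables and split by whether diagnosis came before or after other anticancer therapy. Cases after other chemotherapy should be listed without attribution.

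The cost is one CRF question and one listing, with no new visits or tests. It means slightly more data collection and some requests for outside records. No post-treatment blood count is added, so undiagnosed cases are still missed, and withdrawal of consent still ends contact. The result is a count of known diagnoses and should be described that way.
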